4.6.2 Subgroup Analyses

For lead-in phase primary analysis:

Overview of treatment-emergent adverse events of feminizing side effects, Number of subjects with treatment-emergent study drug-related adverse events of feminizing side effects by preferred term in decreasing order, Number of subjects with treatment-emergent study drug-related adverse events of feminizing side effects by worst CTCAE grade will be presented for the <=50% and >50% week 12 testosterone increase subgroups.

4.7. Interim Analyses

No group sequential interim analyses are planned. However, the analysis will be conducted at three junctures as described in Section 1.

4.8. Changes to Protocol-planned Analyses

There are no changes to the analyses described in the protocol.

ARAMON V3.0 Page: 20 of 31

5. Sample Size Determination

The sample sizes corresponding to the planned analysis methodology are provided below.

Lead-in Phase

Approximately 25 participants will be assigned to darolutamide to achieve at least 20 evaluable participants. This sample size will help estimate the mean percent change in serum testosterone level at 12 weeks with a 95% confidence interval having a half-width of no more than 25%, assuming a true mean percent increase of less than 45% and a standard deviation of 65%. This assessment uses a log normal distribution for percent change.

Randomized Phase

Contingent on the results of the evaluation in Section 1.2.1, the randomized phase statistical assumptions may be revised, or the study could be terminated after lead-in.

Should the study continue to the Randomized phase unmodified, a maximum of 40 participants (20 per arm) will be randomly assigned to study treatment (darolutamide or enzalutamide) such that approximately 34 evaluable participants complete the study. The randomized stage will require a sample size of 20 per group to provide 85% power to test the null hypothesis of no difference between groups on mean percent change at the two-sided 0.05 level. This assessment is based on a mean percent change in Testosterone from baseline and Standard Deviation for the Darolutamide arm of 45% and 65% versus 110% and 75% respectively for Enzalutamide and assumes a log normal distribution for percent change.

ARAMON V3.0 Page: 21 of 31

6. Supporting Documentation

6.1. Population Characteristics

6.1.1 Disposition of participants

Overall summaries will be presented for the lead-in phase, and by treatment arm as well for the randomized phase.

The number and the percentages of participants for the following will be summarized:

- Screened, Evaluable and Safety populations
- Discontinued from screening along with the primary reason for discontinuation
- Discontinued from treatment along with the primary reason for discontinuation
- Discontinued from active follow-up along with the primary reason for discontinuation

6.1.2 Demographics and baseline characteristics

Overall descriptive summaries of demographics and baseline characteristics will be presented for the lead-in phase, and by treatment arm as well for the randomized phase on the Evaluable population.

The following demographic data will be summarized:

- Age (years)
- Age category ($<65, 65-74, 75-84, \ge 85 \text{ years}$)
- Ethnicity
- Race
- Weight (kg)
- BMI (kg/m²)

The following baseline characteristics will be summarized:

- ECOG Performance Status
- Stage of prostate cancer at initial diagnosis
- Gleason score of prostate cancer (<8, \ge 8) at initial diagnosis
- Stage of prostate cancer at study entry
- Serum testosterone group ($< 150 \text{ ng/dL}, \ge 150 \text{ ng/dL}$)
- Time from initial diagnosis to first dose of study drug (months)
- Bone lesions at baseline (Y/N)
- Number of bone lesions at baseline
- Hepatic function at baseline:
 - o Normal: Total bilirubin and AST \leq upper limit of normal (ULN)

ARAMON V3.0

o Mild impairment: Total bilirubin > ULN to 1.5 x ULN or (Total bilirubin ≤ ULN and AST > ULN)

Page: 22 of 31

- o Moderate impairment: Total bilirubin > 1.5 to 3 x ULN, any AST
- Severe impairment: Total bilirubin > 3 x ULN, any AST.
- Estimated glomerular filtration rate (eGFR) at baseline:
 - o eGFR = $[(140 Age) \times Weight/(72 \times Creatinine)]$.

The following baseline lab values, assessed in secondary and exploratory endpoints, will be summarized in a separate baseline table:

- Serum testosterone
- Free testosterone
- PSA
- Sex hormones
- Fat and glucose metabolism
- FACT-P
- Bone turnover
- Physical function

6.1.3 Prior anti-cancer therapies

The prior systemic anti-cancer therapy summaries and summaries of prior radiotherapies and surgeries will be presented for the lead-in phase, and by treatment arm as well for the randomized phase on the Evaluable population.

6.1.4 Important protocol deviations

The number of participants with important protocol deviations will be presented by treatment arm and overall. The frequencies of each important protocol deviation will be presented by treatment arm and overall. All COVID-19 pandemic related protocol deviations are considered important protocol deviations and will be presented by treatment arm and overall.

Page: 23 of 31

ARAMON V3.0

Appendix 1: Imputation rule for partial missing dates

Partial Dates Imputation Rule	Impute partial AE Start Date	Impute partial AE Stop Date
The day missing only	IF AESTDT year and month is same as TRTSDT year and month, then impute AESTDT= TRTSDT	IF AEENDT year and month is same as last known alive date (LKAD) year and month, then impute AEENDT= LKAD
	ELSE IF AESTDT year and month is before TRTSDT year and month, then AESTDT= last date of the month	ELSE impute AEENDT= last date of the month
	ELSE IF AESTDT year and month is after TRTSDT year and month, then AESTDT= first date of the month	
Both day and month missing	IF AESTDT year is same as TRTSDT year, then impute AESTDT=TRTSDT	IF AEENDT year is same as last known alive date (LKAD) year, then impute AEENDT= LKAD
	ELSE IF AESTDT year is before TRTSDT year, then impute AESTDT=31DECYYYY	ELSE impute AEENDT=31DECYYYY
	ELSE IF AESTDT year is after TRTSDT year, then impute AESTDT=01JANYYYY	
Completely missing	No need to impute, try to query the sites by DM	No need to impute, try to query the sites by DM
Additional criteria to meet	 AE start date <= AE stop date The imputed dates <= last known alive date (LKAD) If TRTSDT is missing, use RANDDT as reference date 	

Appendix 2: Scoring procedures for FACT-P

FACT-P Scoring Guidelines (Version 4)

Instructions: 1. F

- 1. Record answers in "item response" column. If missing, mark with an X
- 2. Perform reversals as indicated and sum individual items to obtain a score.

ARAMON V3.0

3. Multiply the sum of the item scores by the number of items in the subscale, then divide by the number of items answered. This produces the subscale score.

Page: 24 of 31

- 4. Add subscale scores to derive total scores (TOI, FACT-G & FACT-P).
- 5. The higher the score, the better the QOL.

Subscale	Item Code	Revers	e item?	Item response	Item Sc	ore
PHYSICAL	GP1	4	_		=	
WELL-BEING	GP2	4	_		=	
(PWB)	GP3	4	_		=	
(2 11 2)	GP4	4	_		=	
	GP5	4	_		=	
Score range: 0-28	GP6	4	_		=	
	GP7	4	_		=	
		•				
				Sum individual item	scores:	
				Multip e by number of items an	oly by 7:	
			Divid	e by number of items an	iswered:	=PWB subscale
score						
SOCIAL/FAMILY	GS1	0	+		=	
WELL-BEING	GS2	0	+		=	
(SWB)	GS3	0	+		=	
(2.77)	GS4	0	+		=	
	GS5	0	+		=	
Score range: 0-28	GS6	0	+		=	
Score range. 0 20	GS7	0	+		=	
						
				Sum individual item	scores:	
				Multip	ly by 7:	
			Divide	by number of items an	swered:	=SWB subscale
score						
EMOTIONAL	GE1	4	-		=	
WELL-BEING	GE2	0	+		=	
(EWB)	GE3	4	-		=	
	GE4	4	-		=	
Score range: 0-24	GE5	4	-		=	
Score range. 0-24						
	GE6	4	-		=	
				Sum individual item	scores:	
				Multip	ly by 6:	
			Divide	by number of items an	swered:	= EWB subscale
score						
FUNCTIONAL	GF1	0	+		=_	
WELL-BEING	GF2	0	+		=	
(FWB)	GF3	0	+		=	
	GF4	0	+		=	
	GF5	0	+		=	
Score range: 0-28	GF6	0	+		=	
	GF7	0	+		=	
				Sum individual item	scores:	

ARAMON V3.0 Page: 25 of 31

Multiply by 7:	
Divide by number of items answered:	=FWB subscale score

Subscale	Item Code	Reverse ite	m?	Item response	Item Score
PROSTATE	C2	4	_		=
CANCER	C6	0	+		=
SUBSCALE	P1	4	-		=
(PCS)	P2	4	-		=
	P3	4	-		=
0.40	P4	0	+		=
Score range: 0-48	P5	0	+		=
	P6	4	-		=
	P7	4	-		=
	BL2	4	-		=
	P8	4	-		=
	BL5	0	+		=

Sum individual item scores:_____ Multiply by 12: _____ Divide by number of items answered: _____=PC Subscale score

To derive a FACT-P Trial Outcome Index (TOI):

Score range: 0-104 $\frac{+}{(PWB \text{ score})} + \frac{+}{(FWB \text{ score})} + \frac{-}{(PCS \text{ score})} = \frac{-}{-} = \frac{-}{FACT-P \text{ TOI}}$

To Derive a FACT-G total score:

Score range: 0-108

+ ____ + ___ + ___ + ___ = ___ = FACT-G Total score

(PWB score) (SWB score) (EWB score)

To Derive a FACT-P total score:

Score range: 0-156

+ + + + + + + + + + + + + + + = = = FACT-P Total score
(PWB score) (SWB score) (EWB score) (FWB score) (PCS score)

Appendix 3: Scoring for PROMIS

To find the total raw score for a short form with all questions answered, sum the values of the response to each question. For example, for the adult 8-item form, the lowest possible raw score is 8; the highest possible raw score is 40. In cases where individual items are skipped, the total raw scores can be prorated using the average of the raw scores of the complete items. This is acceptable as long as more than 50% of the items were answered at that specific visit. The prorated total raw scores with decimals should be rounded to the nearest whole number to translate to the corresponding T-score.

ARAMON V3.0 Page: 26 of 31

The tables below are used to translate the total raw score into a T-score for each participant. The T-score rescales the raw score into a standardized score with a mean of 50 and a standard deviation (SD) of 10. Therefore, a person with a T-score of 40 is one SD below the mean.

| Fatigue 8a - Adult v1.0 | | | | |
|-----------------------------------|---------|-----|--|--|
| Short Form Conversion Table | | | | |
| Raw | Ticcoro | SE* | | |
| Score | T-score | 3E | | |
| 8 | 33.1 | 4.8 | | |
| 9 | 38.5 | 2.7 | | |
| 10 | 41.0 | 2.2 | | |
| 11 | 42.8 | 2.0 | | |
| 12 | 44.3 | 1.9 | | |
| 13 | 45.6 | 1.8 | | |
| 14 | 46.9 | 1.8 | | |
| 15 | 48.1 | 1.8 | | |
| 16 | 49.2 | 1.8 | | |
| 17 | 50.4 | 1.8 | | |
| 18 | 51.5 | 1.7 | | |
| 19 | 52.5 | 1.7 | | |
| 20 | 53.6 | 1.7 | | |
| 21 | 54.6 | 1.7 | | |
| 22 | 55.6 | 1.7 | | |
| 23 | 56.6 | 1.7 | | |
| 24 | 57.5 | 1.7 | | |
| 25 | 58.5 | 1.7 | | |
| 26 | 59.4 | 1.7 | | |
| 27 | 60.4 | 1.7 | | |
| 28 | 61.3 | 1.7 | | |
| 29 | 62.3 | 1.7 | | |
| 30 | 63.3 | 1.7 | | |
| 31 | 64.3 | 1.7 | | |
| 32 | 65.3 | 1.7 | | |
| 33 | 66.4 | 1.7 | | |
| 34 | 67.5 | 1.7 | | |
| 35 | 68.6 | 1.7 | | |
| 36 | 69.8 | 1.8 | | |
| 37 | 71.0 | 1.8 | | |
| 38 | 72.4 | 2.0 | | |
| 39 | 74.2 | 2.4 | | |
| 40 | 77.8 | 3.7 | | |
| *CE - Standard Error on T-score ! | | | | |

^{*}SE = Standard Error on T-score!

| A -114 O | 0 Di | | | | |
|-----------------|--|-----------|--|--|--|
| | Adult v2.0 – Physical Function 6b Short Form Conversion Table | | | | |
| Raw | Onn Conversion | Table | | | |
| Summed
Score | T-score | SE* | | | |
| 6 | 21.0 | 3.8 | | | |
| 7 | 25.0 | 2.7 | | | |
| 8 | 27.1 | 2.4 | | | |
| 9 | 28.8 | 2.2 | | | |
| 10 | 30.1 | 2.1 | | | |
| 11 | 31.3 | 2.0 | | | |
| 12 | 32.3 | 2.0 | | | |
| 13 | 33.2 | 1.9 | | | |
| 14 | 34.2 | 1.9 | | | |
| 15 | 35.0 | 1.9 | | | |
| 16 | 35.9 | 1.9 | | | |
| 17 | 36.8 | 1.9 | | | |
| 18 | 37.6 | 1.9 | | | |
| 19 | 38.5 | 1.9 | | | |
| 20 | 39.3 | 1.9 | | | |
| 21 | 40.2 | 1.9 | | | |
| 22 | 41.2 | 1.9 | | | |
| 23 | 42.1 | 1.9 | | | |
| 24 | 43.2 | 2.0 | | | |
| 25 | 44.3 | 2.0 | | | |
| 26 | 45.6 | 2.2 | | | |
| 27 | 47.1 | 2.3 | | | |
| 28 | 48.9 | 2.7 | | | |
| 29 | 51.3 | 3.0 | | | |
| 30 | 59.0 | 6.2 | | | |
| *SE = Standar | d Error on T-sco | re metric | | | |

PROMIS Physical Function 6b form

PROMIS Fatigue 8a form

ARAMON V3.0 Page: 27 of 31

Appendix 4: Randomized phase primary endpoint analysis for natural logarithm transformed Testosterone

Following data structure will be obtained for the Input dataset LN_DATA. LN_Change will be the difference between the LN(Testosterone) values at Visit 12 from the LN value at baseline.

```
Subjid trt LN_Change
Daro 0.5
Daro 0.9
ENZA 0.5
ENZA 0.8
```

The following SAS code will be used for the two-sample t-test.

```
PROC TTEST DATA=LN_DATA SIDES=2 ALPHA=0.05 H0=0;
CLASS TRT;
VAR LN_CHANGE;
RUN:
```

Appendix 5: Lead-in phase analysis for natural logarithm transformed Testosterone and other endpoints using the log transformation

For the primary end point analysis, PROC TTEST procedure similar to Appendix 4: Randomized phase primary endpoint analysis for natural logarithm transformed Testosterone will be used without the CLASS statement.

For the lead-in phase, the following data structure will be obtained for the input dataset LN_DATA to Proc Mixed. LN_Change will be the difference between the LN(Testosterone) values at Visit from the LN value at baseline. During the lead-in phase there will be no enzalutamide data.

```
Subjid trt
           visit LN Change
          WK2 0.5
     Daro
     Daro WK4 0.9
     Daro
          WK8 1.3
     Daro
          WK16 1.6
          WK24 1.7
     Daro
     Daro WK36 1.7
     Daro
          Wk52 1.6
     Daro
          WK2 0.4
     Daro WK4 1.3
```

Following PROC Mixed code will be used.

```
PROC MIXED DATA = LN_DATA;
CLASS VISIT SUBJID;
```

ARAMON V3.0 Page: 28 of 31

```
MODEL LN_CHANGE = VISIT /DDFM = KR;
RANDOM SUBJID;
REPEATED / TYPE = TOEP SUBJECT=SUBJID;
LSMEANS VISIT/ CL;
RUN;
```

Then the estimate for VISITS WK24 and WK52 will be retained. The dataset will have 2 lines. The fold change pair for each fold change (FC) can be computed as:

```
FC = EXP(Estimate);

LCL_FC = EXP(Estimate - StdErr*quantile('T', .975, DF));

UCL_FC = EXP(Estimate + StdErr*quantile('T', .975, DF));
```

These fold changes can be converted to Percent Change as:

```
PC = (FC-1)*100;

LCL_PC = (LCL_FC -1)*100;

UCL_PC = (UCL_FC -1)*100;
```

Similar code will be used for the other endpoints using the same transformation.

Appendix 6: Randomized phase analysis for natural logarithm transformed Testosterone and other endpoints using the log transformation

The following data structure will be obtained for the input dataset LN_DATA to Proc Mixed. LN_Change will be the difference between the LN(Testosterone) values at Visit from the LN value at baseline.

```
Subjid trt
                LN Change
          visit
     Daro WK2 0.5
     Daro
          WK4 0.9
     Daro WK8 1.3
     Daro WK16 1.6
     Daro WK24 1.7
     Daro WK36 1.7
          Wk52 1.6
     Daro
     Daro WK2 0.4
     Daro WK4 1.3
     ENZA WK2 0.5
     ENZA WK4 2.2
     ENZA WK8 2.6
     ENZA WK16 2.8
```

The following PROC Mixed code will be used.

ARAMON V3.0 Page: 29 of 31

```
PROC MIXED DATA = LN_DATA;
CLASS TRT VISIT SUBJID;
MODEL LN_CHANGE = TRT|VISIT /DDFM = KR;
RANDOM SUBJID(TRT);
REPEATED / TYPE = TOEP SUBJID(TRT);
LSMEANS TRT*VISIT/ DIFF SLICE = VISIT;
RUN;
```

Output the dataset created by LSMEANS. The data will be of the form:

| Obs | Effect | Trt | Visit | _Trt | _Visit | Estimate | StdErr | DF | t-value F | Probt |
|-----|-----------|------|-------|------|--------|----------|--------|-----|-----------|-------|
| 1 | TRT*VISIT | Daro | WK2 | Daro | WK4 | 0.4 | 0.3 | XXX | XXX | 0.xx |
| 2 | TRT*VISIT | Daro | WK2 | Daro | WK8 | 0.8 | 0.32 | XXX | XXX | 0.xx |
| | | | | | | | | | | |
| | TRT*VISIT | Daro | WK2 | ENZA | WK2 | -0.2 | 0.31 | XXX | xxx | 0.xx |
| | | | | | | | | | | |
| | TRT*VISIT | Daro | WK52 | ENZA | WK52 | 0.4 | 0.3 | XXX | XXX | 0.xx |

From this dataset the records where 'Trt NE _Trt', where Trt = 'Daro', where 'Visit = _Visit' and Visit IN ('WK24','WK52") will be selected. This will select the two records where we are reporting results per the secondary objective. The fold change ratio (FCR) and the lower (LCL) and upper (UCL) confidence intervals for the fold change ratio will be obtained as:

```
FCR = EXP(Estimate);

LCL_FCR = EXP(Estimate - StdErr*quantile('T', .975, DF));

UCL_FCR = EXP(Estimate + StdErr*quantile('T', .975, DF))));
```

For fold change (FC) within treatment, the PROC MIXED will be repeated above with the following LSMEANS statement:

LSMEANS TRT*VISIT/CL;

Then the estimate for the Daro and ENZA for VISITS WK24 and WK52 will be retained. The dataset will have 6 lines. The fold change pair for each FCR can be computed as

```
FC = EXP(Estimate);

LCL_FC = EXP(Estimate - StdErr*quantile('T', .975, DF));

UCL_FC = EXP(Estimate + StdErr*quantile('T', .975, DF));
```

These fold changes can be converted to Percent Change as:

```
PC = (FC-1)*100;
LCL_PC = (LCL_FC -1)*100;
UCL_PC = (UCL_FC -1)*100;
```

Similar code can be used for the other endpoints using the same transformation.

ARAMON V3.0 Page: 30 of 31

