4.3.1.1 Lead-in Phase

• Testosterone at weeks 24 and 52:

ARAMON V3.0 Page: 15 of 31

The differences between the log transformed data at the visit and baseline will be estimated with 95% Confidence Intervals using SAS PROC MIXED with the ESTIMATE statement. These will be transformed to mean percent change and 95% confidence intervals using the same steps as for the primary analysis in the lead-in phase. SAS code will be similar to code shown in Appendix 5: Lead-in phase analysis for natural logarithm transformed Testosterone and other endpoints using the log transformation. Results for testosterone at week 24 and 52 will be summarized in a similar manner to the primary endpoint and depicted graphically over time with 95% confidence intervals at each visit.

• PSA responses:

o Undetectable PSA response

Undetectable PSA is defined as a baseline PSA value above the 0.2 ng/mL detection limit and a post baseline PSA level below 0.2 ng/mL, confirmed by a second subsequent PSA value below 0.2 ng/mL 3 or more weeks later, with all potential PSA values between the initial date and the confirmation date below 0.2 ng/mL.

The undetectable PSA response is defined as the number of participants with undetectable PSA divided by the total number of participants evaluable. The undetectable PSA response will be summarized at 4, 12, 24, 36 and 52 weeks.

o PSA50, PSA90

PSA50 is defined as a baseline PSA value above the 0.2 ng/mL detection limit and a post baseline \geq 50% reduction of the PSA level compared to the baseline value, confirmed by a second subsequent PSA value with a \geq 50% reduction from baseline 3 or more weeks later, with all potential PSA values between the initial date and the confirmation date showing a \geq 50% reduction from baseline. PSA90 is defined in the same way with 90% reduction.

The PSA50 response is defined as the number of participants with PSA50 divided by the total number of participants evaluable. The PSA90 response is defined the same way. PSA50 and PSA90 will be summarized at 4, 12, 24, 36 and 52 weeks.

In addition, descriptive statistics will be provided for PSA maximum percent decline of \geq 50%, \geq 90% from baseline at any time on study.

• Analysis of AEs:

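### The PROC MIXED code in SAP Appendices 5 and 6 is wrong as printed (no SUBJECT= in Appendix 6, no visit effect, redundant RANDOM term); the effect is small and confined to secondary and exploratory results

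*SAP*

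**What the plan says.** For the randomized phase, Appendix 6 gives the fixed part as "MODEL LN_CHANGE = TRT|VISIT /DDFM = KR", followed by "RANDOM SUBJID(TRT" and "REPEATED / TYPE = TOEP SUBJID(TRT" (the last two lines close with a parenthesis and semicolon). For the lead-in phase, Appendix 5 prints "REPEATED / TYPE = TOEP SUBJECT=SUBJID", also beside a RANDOM subject statement. Nothing stands before the slash in either REPEATED statement.

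The status of the code is stated in two ways. SAP 4.3.1.1 says "SAS code will be similar to code shown in Appendix 5", and 4.3.1.2 says the same of Appendix 6. The appendices are firmer: Appendix 5 says "Following PROC Mixed code will be used", and Appendix 6 has an equivalent sentence.

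Appendix 6 then keeps the two arms' estimates at weeks 24 and 52 and says "The dataset will have 6 lines". Its upper limit is printed as "UCL_FCR = EXP(Estimate + StdErr*quantile('T', .975, DF" with a run of closing parentheses. Both data layouts label the last visit `Wk52`, while the Appendix 6 selection asks for `WK52`. Neither layout shows a week-12 row.

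Toeplitz is the only covariance structure named in the protocol (9.4.2) or the SAP. The protocol's summary of changes explains that it was preferred to an unstructured matrix as simpler and more efficient.

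**The concern.** The appendices are the only place where the fixed effects, the Kenward-Roger method and the subject structure are set down, so an error there is an error in the specification.

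- **Missing SUBJECT=.** `SUBJID(TRT)` stands as a bare option. SAS should reject it, so programming would catch it.
- **No visit effect.** This is legal SAS and runs without complaint. Without VISIT, PROC MIXED takes a participant's first row as position 1, the second as position 2, and so on. SAP 4.1.2 rules out estimating or carrying forward missing values, so a gap closes up and later visits take too short a lag.
- **RANDOM subject beside full Toeplitz.** The extra variance cannot be separated from the Toeplitz bands. The marginal model is the same, but convergence and the Kenward-Roger step may suffer.
- **Slips.** A wrong line count and a label mismatch could drop week 52 from the selected records.

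At stake are the intervals and the nominal 0.05 and 0.01 flags for testosterone at weeks 24 and 52, sex hormones, fat and glucose markers and bone markers.

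**Working it through.** The documents give no numerical result for this model to reproduce. Their 85% power belongs to the week-12 t-test and is not touched.

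**1. Line count.** 2 arms x 2 visits (weeks 24 and 52) = 4 lines, not 6.

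**2. RANDOM.** For k visits, Toeplitz has k free bands, and the random intercept adds a constant matrix J. J is the sum of all k bands, so it adds a parameter but no rank:

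| Visits | Parameters with RANDOM | Rank |
|---|---|---|
| 8 (testosterone schedule, Protocol Table 1-4) | 9 | 8 |
| 7 (rows printed in the layouts) | 8 | 7 |
| 5 | 6 | 5 |
| 4 | 5 | 4 |

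Estimates are unchanged in principle. The convergence risk was not tested in SAS.

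**3. How often a lag is wrong.** Testosterone visits are weeks 2, 4, 8, 12, 16, 24, 36 and 52. Week 12 is always present in the evaluable population (SAP Table 3-2). Assumptions: each other visit is missed with chance q = 0.05 or 0.10 (p = 1 - q), and 15% drop out after week 12, evenly over the four later visits. A lag is wrong only if a missed visit lies between two observed ones.

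- Weeks 2, 4, 8 do no harm if any missed visits come first: A = p³ + qp² + q²p + q³.
- Weeks 16 to 52 do no harm if any missed visits come last: B4 = p⁴ + p³q + p²q² + pq³ + q⁴. For dropouts with 0, 1, 2 or 3 later visits still due: B0 = B1 = 1, B2 = p² + pq + q², B3 = p³ + p²q + pq² + q³.
- Share with a wrong lag = 1 - A x [0.85 B4 + 0.15 x mean(B0, B1, B2, B3)].

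q = 0.05: A = 0.9050, B4 = 0.8598, mean(B0..B3) = (1 + 1 + 0.9525 + 0.9050)/4 = 0.9644. The bracket is 0.8755, and 1 - 0.9050 x 0.8755 = **0.208**.

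q = 0.10: A = 0.8200, B4 = 0.7381, mean = (1 + 1 + 0.91 + 0.82)/4 = 0.9325. The bracket is 0.7673, and 1 - 0.8200 x 0.7673 = **0.371**.

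**4. Effect on the week-52 standard error.** I enumerated all missing patterns above, with a constant SD and three assumed correlations over dt weeks. The Toeplitz matrix T was fitted to the true V in the large-sample limit (minimising expected log|T| + tr(T⁻¹V)). The table gives model SE divided by sandwich SE; 1 is correct.

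| Correlation | q | As printed | VISIT named | Difference, points |
|---|---|---|---|---|
| 0.4 + 0.6 exp(-dt/12) | 0.05 | 0.974 | 0.979 | 0.5 |
| exp(-dt/40) | 0.05 | 0.959 | 0.971 | 1.2 |
| 0.4 + 0.6 exp(-dt/12) | 0.10 | 0.963 | 0.972 | 0.9 |
| exp(-dt/40) | 0.10 | 0.941 | 0.963 | 2.2 |
| exchangeable 0.6 | either | 1.000 | 1.000 | 0 |

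Most of the remaining shortfall with VISIT named arises because Toeplitz treats unequally spaced visits as equally spaced. At week 24 the largest shortfall is 2.1% as printed (0.979).

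**5. Label order.** As text, the labels sort WK12, WK16, WK2, WK24, WK36, WK4, WK52, WK8. Naming VISIT with these labels would scramble the lags, so the repair needs levels that sort in time order.

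**The case against.** The strongest defence is that the code is illustrative, since the body of the SAP says only that the code will be similar. That softens the point but does not remove it: the appendices say this code will be used, and the version history records corrections to both, so it is maintained as specification.

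Several other objections stand:

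- The numerical effect is small, and the missing keyword would be found at programming.
- A missing first visit moves every later row equally and leaves all lags right; so does loss at the end. Counting everyone whose rows shift would give 25-44%, which overstates the problem.
- Rescheduling (Protocol 7.3) and unscheduled substitutes (SAP 4.1.3) will fill some gaps.
- The surplus parentheses may be an artefact of reading the PDF; Appendix 5 prints the parallel line correctly. Loss of SUBJECT= in the same way cannot be fully excluded.
- The week-12 row may have been left out of the testosterone layout on purpose, because SAP version 2.0 removed week 12 from that secondary endpoint as redundant. It is still needed for sex hormones and metabolic markers, which SAP 4.3.1.2 analyses at week 12.
- Appendix 6 runs only if the randomized phase goes ahead.

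A reader might also infer that the equal-variance Toeplitz is itself an error. The documents do not support that. The sponsor gave a fair reason for it at this sample size, and no document gives log-scale SDs by visit that contradict it. SAP 4.3.1 already has week 24 and 52 results summarised like the primary endpoint, which includes an SD, although on the raw percent scale.

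**Conclusion.** The point holds as a minor specification defect. Four things are wrong on the page: SUBJECT= is absent in Appendix 6, no visit effect is named in either appendix, RANDOM is redundant in both, and there are slips in the line count and the week-52 label. The visit omission matters most in practice, because it produces no error message.

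Its size rests on assumed missingness (5-10% of intermediate visits, 15% later dropout), 8 testosterone visits, constant SD and assumed correlations. Omitting VISIT then costs about 0.5 to 2.2 points of week-52 standard error when correlation decays with time, and nothing when it is exchangeable. For other markers the visits entering the model are not stated, so no figure is offered.

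It would be wrong to conclude that the main result or the decision to proceed is compromised. The primary two-sample t-test (SAP 4.2.1.2) and the binding week-12 condition use neither program.

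**What to change.** Edit the SAP before database lock:

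1. Delete RANDOM in both appendices.
2. Write `REPEATED VISIT / TYPE=TOEP SUBJECT=SUBJID(TRT)` in Appendix 6, and the same with `SUBJECT=SUBJID` in Appendix 5.
3. Code VISIT so that its levels sort in time order (numeric week, or zero-padded labels such as WK02), and change the printed selection of weeks 24 and 52 to match.
4. Correct 6 lines to 4, use one label for week 52, and check the parentheses against the source file.
5. State which visits enter the model for each endpoint, with week 12 included where week 12 is analysed.

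Keep Toeplitz as the pre-specified main model. The cost is a few lines of text, with no new data and no protocol amendment.

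Optional, and not a correction: add a visit-wise t-test at weeks 24 and 52 by the Appendix 4 method as a sensitivity analysis, because it does not need equal variance across visits. Its standard error is about 2-7% larger under the missingness assumed above, since it uses only participants observed at that visit; it should not replace the mixed model.
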